### **8.3 CONSENT AND ASSENT PROCESSES AND DOCUMENTATION**

Consent forms are attached. Two consent forms will be used for this study. Participants will initially agree to allow their blood to be tested for HLA-A\*0201 positivity. The process for obtaining patients' consent for HLA typing may involve telephone contact only. The study will be explained to the prospective patient and any questions answered. The consent form will be signed and witnessed and returned with the blood sample for HLA typing to the NIH by FEDEX. If the patient is HLA-A\*0201 positive they will be invited for a screening visit at the NCI to be evaluated for protocol eligibility. Following eligibility screening, each patient will be discussed with the Principal Investigator or the Lead Associate Investigator. Eligible patients will be presented with a detailed description of the study protocol plan and treatment. The specific requirements, objectives, risks, alternatives, time commitments and potential benefits will be reviewed with the patient. A copy of the Informed Consent will be provided to the patient for their review. The patient will be reassured that participation in this study is entirely voluntary and that they may withdraw or decide against receipt of vaccination at any time without adverse consequences. The Principle Investigator, Lead Associate Investigator or their designee will summarize the screening results and answer any questions prior to obtaining Informed Consent.

## 9 PHARMACEUTICAL INFORMATION

### 9.1 SARGRAMOSTIM

#### 9.1.1 Product Description

The GM-CSF to be used in this study is glycosylated, recombinant human Granulocyte-Macrophage Colony Stimulating Factor (rhu GM-CSF) (brand name Leukine®). This rhu GM-CSF is an altered form of the native molecule: the position 23 arginine has been replaced with a leucine to facilitate expression of the protein in yeast (*Saccharomyces cerevisiae*) and the carbohydrate moiety may be different from the native protein. The Clinical Center Pharmacy will purchase commercially available sargramostim. Rhu GM-CSF will be used both as an ancillary product for the maturation of dendritic cells and for administration to patients with peptide vaccination.

#### 9.1.2 Formulation and Preparations

- A.)** Lyophilized LEUKINE is a sterile, white, preservative-free powder (250 mcg) that requires reconstitution with 1 mL Sterile Water for Injection, USP or 1 mL Bacteriostatic Water for Injection, USP. Reconstituted lyophilized LEUKINE is a clear, colorless liquid suitable for subcutaneous injection or intravenous infusion. The vial of lyophilized LEUKINE contains 250 mcg ( $1.4 \times 10^6$  IU/vial) sargramostim, 40 mg/mL mannitol, USP; 10 mg/mL sucrose, NF; and 1.2 mg/mL tromethamine, USP, as excipients. Biological potency is expressed in International Units (IU) as tested against the WHO First International Reference Standard. The specific activity of LEUKINE is approximately  $5.6 \times 10^6$  IU/mg.
- B.)** Sargramostim solution is a sterile, preserved (1.1% benzyl alcohol) injectable 500 mcg/ml solution.

#### 9.1.3 Stability and Storage

- A.)** **Lyophilized** LEUKINE should be refrigerated at 2 to 8° C (36 to 46° F) and is stable for at least eighteen months. It should not be frozen, shaken or used beyond the expiration date printed on the vial. LEUKINE reconstituted with 1.0 ml of Sterile Water for Injection, USP (without preservative) should be administered as soon as possible and within 6 hours following reconstitution. Reconstituted solutions prepared with Bacteriostatic Water for Injection USP (0.9% benzyl alcohol) may be stored for up to 20 days at 2 to 8° C prior to use. The contents of vials reconstituted with different diluents should not be mixed together.
- B.)** **Sargramostim solution: store intact vials in the refrigerator (2°C-8°C). Do not freeze or shake the vial.**

#### 9.1.4 Administration Procedures

- A.) Lyophilized LEUKINE will be used *in vitro* by the Department of Transfusion Medicine for the generation of dendritic cells by the Department of Transfusion Medicine.
- B.) Sargramostim solution (110 mcg or 0.22ml) will be given with Montanide® ISA 51 with TARP peptides as described in Sections 3.2 Vaccine Administration and Sections 9.3.4 and 9.4.4.

#### 9.1.5 Incompatibilities:

Refer to the package insert/PDR/Formulary.

### **9.2 INTERLEUKIN-4 CELLGENIX**

#### 9.2.1 Product Description

Interleukin-4 (IL-4) used in this study is investigational. It is manufactured and supplied by CellGenix (Master File cross reference BB-MF 11269). It will be used as an ancillary product to mature dendritic cells *in vitro* and will not be administered directly to patients. IL-4 exerts important effects on B cells, T cells, macrophages, eosinophils, hematopoietic progenitor cells, endothelial cells and promotes the maturation of dendritic cells. The complementary DNA clone (cDNA), when expressed in E.coli yields a 129 amino acid protein with a molecular weight of 14,957 daltons. IL-4 is a highly purified ( $\geq 95\%$  chromatographically pure), sterile, water-soluble protein.

#### 9.2.2 Formulation and Preparation

RhIL-4 Sterile Powder for Injection is supplied in 100 mcg and 200 mcg vials (containing a total of 120mcg and 240mcg of IL-4, respectively) as a sterile lyophilized powder formulated with glycine, human serum albumin, citric acid, and sodium citrate. Un-reconstituted IL-4 should be kept refrigerated at 2-8°C. 1.2 mL of Sterile Water for Injection USP should be added to each vial of rhIL-4 Sterile Powder for Injection. The vial should be gently agitated to completely dissolve the powder and should be inspected visually for discoloration and particulates prior to use.

#### 9.2.3 Stability and Storage

The reconstituted product should be refrigerated at 2-8°C and should be used within 24 hours.

#### 9.2.4 Administration Procedures

To be used in dendritic cell culture, not administered directly to patients.

#### 9.2.5 Incompatibilities:

None known in culture.

### **9.3 TARP 29-37-9V PEPTIDE (EPIPOPE-ENHANCED) NSC #740704**

#### 9.3.1 Product Description

TARP 29-37-9V is investigational. TARP 29-37-9V is a synthetic HLA-A2-restricted 9-amino acid epitope of the tumor associated protein TARP, with a single amino acid substitution (valine at position 37, instead of leucine) to increase its binding affinity and immunogenicity. Amino acid sequence: Phenylalanine-Leucine-Arginine-Asparagine-Phenylalanine-Serine-Leucine-Methionine-Valine (FLRNFSLMV)

Molecular Weight: 1126.4

#### 9.3.2 Formulation and Preparation

The peptide is manufactured by NeoMPS, Inc., [name]. The peptide is vialled by the Clinical Center Pharmacy as a 5 mL siliconized sterile amber type 1 glass vial with a Teflon-lined stopper containing 0.5 mL of a sterile clear solution. Each mL

contains 2.2 mg of TARP:29-37(37V) Peptide and 0.5 mL of trifluoroacetate 0.05% v/v.

### 9.3.3 Stability and Storage

Store the finished injectable dosage forms in the freezer (-70°C) for long-term storage. Intact vials are stable for at least 6 months when stored at controlled room temperature (15°C – 30°C), at least 9 months when stored in the refrigerator (2°C – 8°C), and for at least 36 months when stored in the freezer (-10°C to -25°C and -70°C). The peptide vial contains no preservatives; once the peptide vial is entered, discard unused peptide solution after 3 hours. Vaccine emulsions consisting of peptide admixed with Montanide® ISA 51 VG are stable for up to 3 hours, but should be administered as soon as possible following preparation.

### 9.3.4 Administration Procedures

Preparation and administration of Epitope-Enhanced TARP with Montanide® ISA 51 VG and sargramostim: Each vial of TARP 29-37-9V peptide is in aqueous solution containing 0.5ml of peptide at a concentration of 2.2 mg/ml, for a total of 1.1mg peptide per vial. Sargramostim solution, 110 micrograms, (0.22 mL) and 0.1 mL of 10x saline will be added to the vial of peptide for a total aqueous peptide volume of 0.82 ml. Prepare the peptide emulsion by injecting the 0.82ml aqueous TARP 29-37-9V peptide solution into 0.8 mL of Montanide® ISA 51 VG as outlined in Section 9.6.6 Syringe Method of Emulsification. The total volume of peptide emulsion will be 1.62 ml. Withdraw a total of 1.5 mL (~1.0 mg of peptide) for administration by deep subcutaneous injection in one or two equal volumes into the anterior thigh.

Administration: Injections will preferentially be administered in the anterior thigh. The upper arm may be used if necessary. The same extremity will be used for each dose of peptide administered on any given day but the extremities may be rotated.

### 9.3.5 Incompatibilities

None known.

### 9.3.6 Reported Adverse Events and Potential Risks

Common adverse events reported with peptides emulsified with Montanide® ISA 51 VG have consisted of fatigue, fever, flushing, injection site reactions including pain, erythema and induration; localized swelling, rare granuloma formation. Other reported possible adverse events include chills/rigors, transient increases in liver transaminases, headache, rash, and pruritis. TARP is a 58 amino acid protein found on cells of prostate origin and is over expressed in over 90% of patients with prostate cancer and about half of patients with breast cancer. Because the peptide mimics portions of a prostate protein found naturally in the body, there is a chance for development of an autoimmune reaction to it and may result in the possible development of inflammation in the prostate gland.

### 9.3.7 Special Handling

The peptide is NOT a cytotoxic or infectious agent and requires no special handling.

## 9.4 TARP 27-35 (WILD TYPE) NSC#740703

### 9.4.1 Product Description

TARP 27-35 is a synthetic HLA-A2-restricted 9-amino acid epitope of the tumor-associated protein TARP.

Amino acid sequence: Phenylalanine-Valine-Phenylalanine-Leucine-Arginine-Asparagine-Phenylalanine-Serine-Leucine (FVFLRNFSL)

Molecular Weight: 1142.4

#### 9.4.2 Formulation and Preparation

The peptide is manufactured by NeoMPS, Inc., [name]. The peptide is vialled by the Clinical Center Pharmacy as a 5 mL siliconized sterile amber molded glass vial containing a sterile white lyophilized powder. Each vial contains 1.1 mg of TARP:27-35 peptide and Mannitol.

#### 9.4.3 Stability and Storage

Store the finished injectable dosage forms in the freezer (-70°C) for long-term storage. Intact vials are stable for at least 6 months when stored at controlled room temperature (15°C – 30°C) or in the refrigerator (2°C – 8°C), and for at least 36 months when stored in the freezer (-10°C to -25°C and -70°C). The peptide vial contains no preservatives; once the peptide vial is entered, discard unused peptide solution after 3 hours. Vaccine emulsions consisting of peptide admixed with Montanide® ISA 51 are stable for up to 3 hours, but should be administered as soon as possible following preparation.

#### 9.4.4 Administration Procedures

Preparation and administration of WT TARP with Montanide® ISA 51 VG and sargramostim: Each vial of WT TARP 27-35 peptide contains 1.1 mg as a lyophilized powder. It is reconstituted in 0.5 mL of Sterile Water for Injection, USP to yield a final concentration of 2.2 mg/mL. Sargramostim solution, 110 micrograms, (0.22 mL) and 0.1 mL of 10x saline will be added to the vial of peptide for a total aqueous peptide volume of 0.82 mL. Prepare the peptide emulsion by injecting the 0.82 mL aqueous WT TARP 27-35 peptide solution into 0.8 mL of Montanide® ISA 51 as outlined in Section 9.6.6 Syringe Method of Emulsification. The total volume of peptide emulsion will be 1.62 mL. Withdraw a total of 1.5 mL (~1.0 mg of peptide) for administration by deep subcutaneous injection in one or two equal volumes into the anterior thigh.

Administration: Injections will preferentially be administered in the anterior thigh. The upper arm may be used if necessary. The same extremity will be used for each dose of peptide administered on any given day but the extremities may be rotated.

#### 9.4.5 Incompatibilities

None known.

#### 9.4.6 Reported Adverse Events and Potential Risks

Common adverse events reported with peptides emulsified with Montanide® ISA 51 VG have consisted of fatigue, fever, flushing, injection site reactions including pain, erythema and induration; localized swelling, rare granuloma formation. Other reported possible adverse events include chills/rigors, transient increases in liver transaminases, headache, rash, and pruritis. TARP is a 58 amino acid protein found on cells of prostate origin and is over expressed in over 90% of patients with prostate cancer and about half of patients with breast cancer. Because the peptide mimics portions of a prostate protein found naturally in the body, there is a chance for development of an autoimmune reaction to it and may result in the possible development of inflammation in the prostate gland.

#### 9.4.7 Special Handling

The peptide is NOT a cytotoxic or infectious agent and requires no special handling.

### 9.5 INFLUENZA VIRUS VACCINE LIVE INTRANASAL

#### 9.5.1 Product Description

The influenza virus vaccine live intranasal (FluMist™) is a live trivalent nasally administered vaccine intended for active immunization for the prevention of influenza. The product is manufactured by MedImmune and will be purchased by the Clinical Center Pharmacy. The previous season's vaccine might be used until the supply for the current influenza season becomes available.

#### 9.5.2 How Supplied

This vaccine contains live attenuated, cold adapted virus from both influenza A and B. Each 0.2 mL dose is formulated to contain  $10^{7.0 \pm 0.5}$  TCID50 (median tissue culture infectious dose) of live attenuated influenza virus reassortants of the strains recommended by the U.S. Public Health Service (USPHS).

#### 9.5.3 Stability and Storage

Influenza virus vaccine live intranasal can be stored for extended periods at 2-8 °C. Influenza virus vaccine live intranasal is a clear to slightly cloudy, colorless to pale yellow liquid; some proteinaceous particulates may be present. The thawed vaccine should not be refrozen.

#### 9.5.4 Administration Procedures

Patients should receive 0.2 ml intranasally of influenza virus vaccine (0.1ml in each nostril) during vaccination. Under no circumstances should the vaccine be administered parenterally. If the vaccinee sneezes after administration of the intranasal vaccine, the dose should *not* be repeated. Influenza virus vaccine live intranasal is contraindicated in patients with known hypersensitivity to any component of the vaccine, including egg or egg products, individuals with a history of Guillan-Barre Syndrome, a known or suspected immunodeficiency disease/condition and individuals with asthma or reactive airway disease or other chronic pulmonary, cardiovascular or metabolic conditions. Vaccine administration should be postponed for a least 72 hours after the acute phase of a febrile and /or respiratory illness.

#### 9.5.5 Special Precautions

Because live attenuated influenza viruses replicate in the nasopharynx of recipients of influenza virus vaccine live intranasal and can be shed in respiratory secretions, the possibility exists that the vaccine viruses can be transmitted to susceptible individuals who have not received the vaccine. The manufacturer states that individuals receiving influenza virus vaccine live intranasal should avoid close contact with immunocompromised individuals for at least 21 days after vaccination. To minimize risk of transmission of attenuated vaccine virus to other Clinical Center patients the following procedures will be adhered to:

- influenza virus vaccine live intranasal will be administered immediately prior to the patient's departure from the Clinical Center.
- The patient will be asked to wear a mask in the process of exiting the building and will be immediately discharged to home.

- Transportation by private taxi to the airport will be authorized to eliminate exposure to other CC patients traveling on the NIH shuttle.
- Patients will be provided with a hand hygiene product as well as tissues.
- Patients will not be authorized to return to the CC until at least 21 days following receipt of their vaccine.
- While away from the CC they will be advised to avoid contact with severely immunosuppressed patients for 7 days after vaccination.

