### **Study Design**

- This is a randomized, prospective, pilot study of vaccination with a mixture of wild type (TARP27-35) and epitope-enhanced (TARP29-37-9V) TARP peptides in HLA-A\*0201 patients with stage D0 prostate cancer.
- Vaccination with TARP peptides admixed with Montanide® ISA 51 VG plus Sargramostim administered by deep subcutaneous injection will be compared with vaccination with TARP peptide-pulsed autologous dendritic cells (DCs) administered intradermally.
- Autologous dendritic cells will be matured from peripheral blood monocytes with Sargramostim, IL-4, IFN- $\gamma$  and LPS and pulsed with wild type and epitope-enhanced TARP peptides.
- Apheresis will be performed on all patients at weeks 0, 24, and 48.
- Randomization and assignment to received TARP peptide vaccine with Montanide® ISA 51 VG plus Sargramostim given by deep subcutaneous injection or TARP peptide-pulsed autologous DCs given ID will be performed at week 0.

- All patients will receive live, attenuated influenza vaccine (FluMist™) when seasonally available at the very end of their week 0 visit as a control vaccine to assess cytotoxic T lymphocyte responses.
- TARP Peptide vaccines will be administered every three weeks at weeks 3, 6, 9, 12, and 15, with a sixth and seventh booster dose of vaccine at Week 48 and 96. Follow-up will be through 144 weeks on study.
- The trial uses an optimal 2-stage design targeting an immunologic response between 10 and 40%. We will initially accrue 9 patients in each arm. If 0-1 patients develop an immunologic response, then no further patients will be enrolled. If 2 or more of these patients develop an immunologic response, we will accrue 11 additional patients for a maximum total of up to 20 patients in each arm. A stopping rule for excessive toxicity will be incorporated.

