### 3.1.1 Study Schema

### 3.2 VACCINE ADMINISTRATION

Following apheresis to remove peripheral blood monocytes for dendritic cell preparation as well as peripheral blood mononuclear cells for flow cytometry and immunologic studies at their week 0 visit, all patients will undergo intranasal vaccination with live attenuated influenza vaccine (FluMist™) when seasonally available. Attenuated influenza vaccine is being administered as a control vaccine to characterize the patient's innate ability to generate immune responses to vaccination. Conserved HLA-A\*0201 restricted cellular and humoral responses to flu matrix peptides have been extremely well characterized regarding antibody titers and the range of ELISPOT responses that are typically observed in normal healthy individuals. Following receipt of the intranasal flu vaccine, patients will be immediately discharged to home and precautions will be taken to minimize the risk of potential transmission to other Clinical Center patients as outlined in Section 9.5

Because live attenuated influenza viruses replicate in the nasopharynx of recipients and can be shed in respiratory secretions, the possibility exists that the vaccine viruses can be transmitted to susceptible individuals who have not received the vaccine. Studies in children 8-36 months of age attending daycare who were randomized to receive a single dose of influenza virus vaccine live intranasal or placebo indicated that 80% of vaccine recipients shed at least 1 vaccine strain; the mean duration of shedding was 7.6 days (range: 1-21 days). The frequency and duration of shedding of vaccine virus strains by individuals 5-49 years of age who receive influenza virus

vaccine live intranasal have not been established. Consequently, study patients will return to the CC at study week 3 which should provide an adequate window to ensure that recipients are unlikely to be shedding attenuated viral vaccine strains.

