## **5 DATA COLLECTION AND EVALUATION**

### **5.1 DATA COLLECTION**

The Vaccine Branch clinical research team will perform real time data collection. The Principal Investigator will be responsible for oversight of the protocol.

All patients enrolled on study will be centrally registered at the NCI Central Registration Office. All on study evaluations must be performed within one week of their scheduled time point as outlined in the study schema ([Appendix 1](#)). Delay in vaccine administration is allowed for up to 3 weeks as outlined in Section [3.3.3](#). Modifications in this policy can be discussed on an individual basis with the Lead Associate Investigator. Research data will be collected in the NCI C3D database.

All AEs, including clinically significant abnormal findings on laboratory evaluations, regardless of severity, will be followed until satisfactory resolution. AEs should be reported up to 30 days following the last dose of study drug.

An abnormal laboratory value will be considered an AE if the laboratory abnormality is characterized by any of the following:

- Results in discontinuation from the study
- Is associated with clinical signs or symptoms
- Requires treatment or any other therapeutic intervention
- Is associated with death or another serious adverse event, including hospitalization.
- Is judged by the Investigator to be of significant clinical impact

**End of study procedures:** Data will be stored according to HHS, FDA regulations, and NIH Intramural Records Retention Schedule as applicable.

**Loss or destruction of data:** Should we become aware that a major breach in our plan to protect subject confidentiality and trial data has occurred, the IRB will be notified.

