HIV Serology								
Hepatitis B Serology								
Hepatitis C Serology								
HTLV-1 Serology								
VDRL								
EKG								
CT Scan /Chest/Abd/Pelvis				X				X
Bone Scan				X				X
Lymphocyte Subsets	X			X				X
Anti-TARP Antibody	X			X				X
NKT Cell Assessment								
Tetramer Staining	X	X	X	X	X	X		X
IFN-γ ELISPOT	X	X	X	X	X	X		X
 Cr CTL Assay#	X	X	X	X	X	X		X
PBMCs for Storage	X	X	X	X	X	X		X
Serum for Storage	X	X	X	X	X	X		X

Notes:

- Screening CT scans of the Chest/Abd/Pelvis and Bone Scans may be performed up to 8 weeks prior to enrollment and at outside institutions.
- All on study assessments can be obtained within +/- one week of scheduled measurement to allow for holidays and unscheduled delays.
- Screening for HLA-A\*0201 positivity will be completed before protocol eligibility screening is initiated. Only HLA-A\*0201 positive patients are brought to NIH for further screening and eligibility assessment.
- FluMist™ vaccination will be given with the seasonal influenza preparation when it is available at the time of enrollment.
- X\*: a 6th dose of TARP peptide vaccine will be administered to those patients with a ≥ 50% increase in PSADT at week 24 or who have confirmed immunologic responses to vaccination by tetramer or IFN-g ELISPOT assays as outlined in Section 5.2.1 Immunologic Response Criteria. A booster dose of TARP peptide vaccine will be administered to all patients at Week 48 and 96 who elect to continue on the extension phase of the study through Week 144..
- #: Cr CTL Assay will be performed at the time points indicated only in those patients with evidence of immunologic reactivity by tetramer staining and/or IFN-γ ELISPOT assays.

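### Section 9.5.5 bars return to the Clinical Center within 21 days of FluMist, but the week 3 visit and its one-week window in Appendix 1 permit an earlier return

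*Combined protocol and SAP*

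**What the plan says.** Section 9.5.5 lists procedures meant to limit transmission of attenuated vaccine virus to other patients at the centre. One of them reads: "Patients will not be authorized to return to the CC until at least 21 days following receipt of their vaccine". No exception is given.

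The Précis (Study Design) places FluMist "at the very end of their week 0 visit as a control vaccine to assess cytotoxic T lymphocyte responses". Section 3.2 puts it after the week 0 apheresis. In the Appendix 1 schedule the FluMist mark and the week 0 apheresis mark both sit in the column for week 0 day 3 or day 5. Week 0 day 1 is a separate column with no FluMist mark. The next column is week 3, when the first TARP vaccine is given.

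Section 3.2 links that return to viral shedding: "study patients will return to the CC at study week 3 which should provide an adequate window". Two passages set the visit window. The notes to Appendix 1 say "All on study assessments can be obtained within +/- one week of scheduled measurement to allow for holidays and unscheduled delays", and Section 5.1 says "All on study evaluations must be performed within one week of their scheduled time point as outlined in the study schema". Neither singles out week 3.

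Section 9.5.5 also contains two statements about contacts. It reports the manufacturer's position that recipients should avoid close contact with immunocompromised people for at least 21 days. It then says that patients, while away from the centre, will be advised to "avoid contact with severely immunosuppressed patients for 7 days after vaccination".

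**The concern.** Section 3.2 appears to treat week 3 as if it were 21 days after FluMist. Appendix 1 places FluMist two or four days after the only day it labels day 1, so the two agree only if the weeks are counted from FluMist, which no section states. The one-week window then allows the visit to be earlier still.

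The rule protects people outside the trial, at a centre that treats immunocompromised patients. Staff who book from Appendix 1 and staff who book from Section 9.5.5 could reach different dates for the same patient.

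There is also a smaller measurement point. Section 3.4.6.1 takes the week 3 blood sample for FluMist responses, so an undefined interval leaves the timing of that control readout loose.

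**Working it through.** The check is a day count.

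**Inputs**
- Minimum interval from FluMist to return: 21 days (Section 9.5.5).
- FluMist day: week 0 day 3 or day 5 (Appendix 1).
- Next visit: week 3 (Section 3.2; Appendix 1).
- Window: plus or minus 7 days (Section 5.1; notes to Appendix 1).
- Assumption for the main count: week 3 is counted from week 0 day 1. The documents give week 3 no study-day number.

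**The plan's own figure.** Section 3.2 regards the week 3 return as leaving enough time. A gap of exactly 21 days results if FluMist is given on day 1 (22 − 1 = 21), where Appendix 1 does not put it, or if week 3 is counted from the day of FluMist.

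**Count from week 0 day 1**
- Week 3 = day 1 + 21 = day 22.
- Nominal gap = 22 − FluMist day.
- Early edge = nominal gap − 7. Late edge = nominal gap + 7.
- Earliest day that satisfies Section 9.5.5 = FluMist day + 21.

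| FluMist day | Nominal gap | Early edge | Late edge | Earliest compliant study day |
|---|---|---|---|---|
| Day 3 | 22 − 3 = 19 | 12 | 26 | 3 + 21 = 24 (2 days after day 22) |
| Day 5 | 22 − 5 = 17 | 10 | 24 | 5 + 21 = 26 (4 days after day 22) |

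**Count from the FluMist day.** Nominal gap 21 days; early edge 21 − 7 = 14; late edge 21 + 7 = 28. The nominal conflict disappears, but the early half of the window still falls short of 21 days.

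**Week 3 read as any of study days 22 to 28.** The gap is 22 − 3 = 19 to 28 − 3 = 25 days after a day 3 dose, and 22 − 5 = 17 to 28 − 5 = 23 days after a day 5 dose. Each range contains days that comply and days that do not.

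**Reach of the window.** The window is written for assessments and evaluations. The week 3 visit includes several of these in Appendix 1: physical examination, CBC, PSA and PBMCs for storage. No note removes that visit from it.

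**Spread of the FluMist-response sample.** Counting from day 1, the schedule and window together allow it between 10 days (day 5 dose, early edge) and 26 days (day 3 dose, late edge) after FluMist.

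**The case against.** The best defence is that the specific rule limits the general one. The Appendix 1 window is permissive and its stated purpose is holidays and unscheduled delays, whereas the return rule in Section 9.5.5 is mandatory and the centre controls authorization. On that reading nobody comes back early. Section 3.2 can also be read as presenting week 3 as the post-FluMist interval, which gives exactly 21 days. Where vaccine timing is discussed (Sections 3.3.3 and 5.1), only delay is addressed.

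Much of this is fair, and it limits what can be claimed. A reader might infer that every FluMist recipient must breach the rule. The documents do not support that: even counting from day 1, study days 24 and 26 lie within a week of day 22, so both rules can be met with a shift of 2 or 4 days. A reader might also take 17 or 19 days as the planned interval, but it depends on a counting convention that the plan never states.

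Nor can the 1-to-21-day shedding range in Section 3.2 be carried over to these patients. It comes from children aged 8 to 36 months, with a mean of 7.6 days, and the same section says shedding at ages 5 to 49 has not been established.

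The 21-day and 7-day contact statements are not a plain contradiction either. One is the manufacturer's and concerns close contact with immunocompromised people. The other is the protocol's own advice and concerns contact with severely immunosuppressed patients while away from the centre. What remains is that no reason is given for the shorter period.

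The defence still leaves a gap. No section states that Section 9.5.5 overrides the window, counts week 3 from FluMist, or exempts the week 3 visit.

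**Conclusion.** The inconsistency is real but modest. Section 9.5.5 requires at least 21 days. The schedule as written permits a return at 12 or 10 days if week 3 is counted from week 0 day 1, or at 14 days if it is counted from FluMist. The early side of the window therefore conflicts with the rule under either count. The nominal day conflicts (19 or 17 days) only under the day 1 count, which is an assumption.

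The schedule permits a breach and does not compel one. Only patients who receive FluMist are affected, and it is given when seasonally available. Any slip in the first TARP vaccination needed to comply is 2 or 4 days on the day 1 count, within the visit window. Nothing in the documents shows an effect on immunologic response, dose-limiting toxicity or PSADT, so the case for correction rests on the safeguard for other patients and on a clear timing for the FluMist-response sample.

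The two contact-avoidance statements are a secondary matter of unexplained difference.

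**What to change.** Reconcile Section 3.2, Section 5.1, Section 9.5.5 and the Appendix 1 schedule and notes on two points:

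- what week 3 is counted from for patients who receive FluMist;
- whether the early side of the one-week window applies to that visit.

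In Section 9.5.5, also reconcile the manufacturer's 21-day statement with the 7-day advice, or give the reason for the difference.

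Which intervals apply is for the sponsor to decide. The cost is one footnote to the schedule and a sentence in the text; sample size and analysis are unchanged.
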